3.1 Primary objective and primary endpoint

The primary objective of the clinical trial is to investigate whether albumin administration and maintenance of serum albumin concentrations of at least 30 g/l in the ICU for up to 28 days after the onset of septic shock will reduce 90-day all-cause mortality, compared to volume replacement therapy without albumin.

The primary endpoint is 90-day all-cause mortality (EMA Guideline CHMP / EWP / 4713/03). Based on the subgroup analysis of the ALBIOS study (24), the potential benefit of albumin administration is most likely to be apparent 90 days after randomization. Based on experience with the previous SepNet study (26, 27), the risk of patients being discharged from hospital 90 days after randomisation, and thus unavailable for follow-up, will not significantly affect data collection at this time point.

3.2 Secondary objectives and secondary endpoints

The purpose of the clinical trial is to secondarily investigate whether albumin administration and the maintenance of serum albumin concentrations of at least 30 g/l for 28 days after the onset of septic shock will influence 28- and 60-day mortality, ICU and hospital mortality rates, organ dysfunction/failure as assessed by the SOFA score, ICU and hospital lengths of stay, as well as ventilator- and vasopressor-free days. A cost-benefit analysis of the volume replacement therapy for the ICU stay up to a maximum of day 28 is another objective of this clinical trial.

Secondary end-points therefore are

- 28- and 60-day mortality,
- ICU and hospital mortality,
- organ dysfunction/failure as assessed by the SOFA-Score: recorded daily up to 28 days in the ICU after randomisation in the study,
- ICU and hospital lengths of stay.
- ventilator- and vasopressor-free days,
- cost-benefit of volume replacement therapy: collection of data on the use of human albumin and other colloids and crystalloids,
- · Total amount of fluid administration and total fluid balance, and
- safety-related parameters: occurrence of AEs and SAEs, especially anaphylactic shock, hypervolaemia, and pulmonary oedema.

4. Trial design

4.1 Description of the clinical trial

The ARISS study is a prospective, multicentre, randomised, controlled, parallel-grouped, open-label, interventional clinical trial (Phase IIIb) according to the German Medicines Act (AMG). Participants are male and female persons ≥ 18 years with septic shock.

4.2 Feasibility of recruitment

The SepNet Study Group is a network of physicians and scientists from around 50 clinics and universities throughout Germany. This interdisciplinary network brings together experts from various disciplines working in the field of clinical and experimental sepsis research. They have considerable experience and interest in clinical trials in sepsis patients. These clinical studies can be performed at the well-established SepNet regional centres and numerous associated centres with interdisciplinary, medical and surgical ICUs. Successful studies carried out by the SepNet study group in the past have proved the ability of this network to perform the ARISS study. Based on estimates of expected recruitment numbers provided by the requested trial sites, it is anticipated that the clinical trial will achieve the required number of cases within the planned recruitment period.

Evaluation of data from the Jena Sepsis Registry (BMBF-ID: 01 E0 1002 and DRKS number: DRKS00008342) was carried out. In this registry, prospective data were collected from all patients with severe sepsis who were admitted to the 4 ICUs of the Jena University Hospital (2 surgical, 1 medical, 1 neurological) between January 2011 and December 2015. A total of 1988 patients with severe sepsis (within 24 hours of the onset of sepsis) were identified, 1478 of whom had septic shock. Only 176 patients had at least one of the exclusion criteria for the ARISS study. Sixty-two patients died or relocated to another facility within 24 hours of the onset of the septic shock. A total of 1,236 patients, i.e., approximately 247 patients per year, would have been suitable for the ARISS clinical trial.

It is estimated that the clinical trial will require 40-50 trial sites to randomise 1,662 patients over 3 years; that is, about 13-14 patients per year per site. The ICUs that have confirmed participation in the ARISS study within the framework of the DFG application stated the possibility of including an average of 141 patients with septic shock. A recruitment rate of up to 21 patients per year per trial centre is, thus, expected. These figures show that the required recruitment figures can be achieved with an adequate safety margin. A drop-out rate of 15% of randomised patients is assumed, resulting in 11-12 patients per year per site and a total of 1412 patients from all sites to be be included in the final evaluation.

4.3 Trial duration

Approximately 36 months are planned for the recruitment of patients.

Depending on the patients, study durations will vary in length. The trial product will be administered for a maximum of 28 study days after randomisation in the ICU.

On day 90 after randomisation, data collection and thus participation in the study will end for the respective patient.

5. Participation in the clinical trial

5.1 Selection of participants

The target population for the clinical trial are male and female patients ≥ 18 years of age with septic shock treated in an ICU.

Screening will be performed daily in the respective trial centres to see whether eligible patients are being treated in the ICUs.

Patients ≥ 18 years of age with septic shock will be approached to obtain informed consent to participate in the study. No patient will be excluded from participation because of sex, race, ethnicity, or sexual preference.

5.1.1 Explanation of sex distribution of the study population

The clinical trial does not involve any sex-specific issues. Patients will be consecutively screened during routine clinical practice for eligibility to participate in the clinical trial and included accordingly. The trial intervention is not sex-dependent and sex-related differences will not be addressed in the trial.

5.1.2 Inclusion criteria

Patients who meet all the following inclusion criteria may be included in this clinical trial:

- Presence of septic shock that meets all the following criteria (1):
 - o Clinically possible, probable or microbiologically confirmed infection according to the definitions of the International-Sepsis-Forums (ISF) (2)
 - o Despite adequate volume therapy, vasopressors are required to maintain mean arterial pressure (MAP) \geq 65 mm Hg for at least 1 hour
 - o Serum lactate concentration > 2 mmol/l (18 mg/dl) despite adequate volume therapy
- Onset of septic shock less than 24 hours prior to study inclusion, so that administration of the initial dose of the trial product is possible within 6-24 hours after the onset of septic shock in the albumin group
- Age: ≥ 18 years
- Written informed consent of the patient or his/her legal representative (guardian) or confirmation of the urgency of participation in the clinical trial and the possible benefit to the patient by an independent consultant or the implementation of other established procedures according to the local regulations of the contributing centre to include patients who are unable to provide informed consent in whom subsequent consent may be obtained retrospectively (for more details see chapter 5.2)
- Patient of childbearing age: negative pregnancy test

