1.1 Overview of the clinical trial

	Randomised controlled multicentre study of albumin	
Title of the trial	replacement therapy in septic shock	
Trial Acronym	ARISS-Study	
Sponsor according to AMG	Friedrich Schiller University Jena	
Sponsor's legal representative (SpB) and principal investigator (LKP)	[name]. [name] Universitätsklinikum Jena Klinik für Anästhesiologie und Intensivmedizin [name] [contact] [contact] E-Mail: [contact]	
EudraCT Number	2018-001874-89	
Study population	Female and male patients ≥ 18 years treated in the intensive care unit (ICU) within 24 hours of septic shock diagnosis	
Study phase	III b	
Trial design	Prospective, multicentre, randomised, controlled, parallel- grouped, open-label, interventional clinical trial according to the German Medicinal Products Act	
Primary target: To investigate whether albumin administration and maintenance of serum albumin concentrations of a 30 g/l in the ICU for up to 28 days after the onset of shock, will reduce total 90-day mortality compared volume replacement therapy without albumin Secondary targets: - To investigate whether albumin administration at maintenance of serum albumin concentrations of 30 g/l in the ICU for up to 28 days after the onset septic shock would influence ICU, hospital, 28-a day mortality rates, rates of organ dysfunction/far assessed by the SOFA score, ICU/hospital length stay, ventilator and vasopressor-free days. - Cost-benefit analysis of volume replacement the		
Primary outcome (primary	from ICU admission until maximum day 28 Primary outcome: 90-day all-cause mortality	
end-point)		
Secondary outcome	Secondary outcomes:	
(secondary end-point)	 - 28- and 60-day mortality, mortality rates in the ICU and during hospitalization, organ dysfunction/failure as assessed by the SOFA score, ICU and hospital length of stay, ventilator and vasopressor free days. 	

ARISS
EudraCT-Nr.: 2018-001874-89
ZKSJ0112_ARISS
UNIVERSITATS
KLINIKUM
Jena

Sample size	 Cost-benefit parameters of volume replacement therapy (albumin, other colloids and crystalloids) Total amount of fluid of fluid administration and total fluid balance in the ICU. Safety related endpoints: Onset of AEs and SAEs, in particular anaphylactic shock, hypervolaemia, pulmonary oedema and sepsis-related clinical events Assuming a 90-day mortality of 50% in the control group without albumin and 42% in the albumin group, 1412 patients need to be evaluated (power: 80%, Chi²Test alpha

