5.2.2 Patients who are unable to consent

Because of the expected high severity of illness in the trial population, most of the eligible patients will be unable to consent. In this case, it will not be possible to obtain written consent from the patient prior to initiating the study-related measures.

In patients with septic shock, early therapy is a crucial determinant of prognosis of these patients. A therapeutic benefit from the intervention -albumin administration in the albumin group- can likely only be demonstrated if the clinical trial is started within the first few hours of the diagnosis of septic shock.

Since, according to international guidelines, early initiation of therapy is one of the essential standard therapies for severe sepsis and septic shock, it may be justified to begin the clinical trial in the existing emergency situation (septic shock) without informed consent of a legal representative or a guardian. According to AMG, participation is legally possible even without informed consent if this cannot be obtained due to an emergency situation. These patients can be included in the study according to § 41 Abs. 1 AMG (29) which states that: if informed consent cannot be obtained because of an emergency situation, treatment indicated to be given without delay to rescue the life of the concerned persons, to restore their health or to minimize their suffering, can be promptly initiated. Consent for further participation must be obtained as soon as possible and reasonable.

In this case, the trial centers should adopt the locally established procedure for including patients who are unable to consent and follow the recommendations of the local ethics committee. The presumed will of the patient should be considered. If she/he would refuse to participate, the patient should not be included in the clinical trial.

Patients unable to consent - with a guardian or legal representative

consent to participate in the clinical trial may be given in writing by the guardian or legal representative. A copy of the act of attorney or the identity card must be kept in the trial centre (ISF or separately).

If the guardian or the legal representative considers that the patient would not have wanted to participate in the trial, or if the guardian or the legal representative refuses participation, the patient will not be included in the clinical trial.

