6.3 Administration of the trial drug (only in the albumin group)

6.3.1 Start dose

Administration of the initial dose of the trial drug must be started within 6 to 24 hours after the beginning of the septic shock. A maximum of 2 hours may elapse between randomisation and the start of administration of the initial dose.

Before the initial dose is given, a blood sample must be drawn to determine the serum albumin concentration.

Starting dose: 60 g human albumin 20% (200 g/l, infusion solution) over 2-3 h

Application: The investigational product will be administered intravenously using an infusion device. The human albumin should not be mixed with other medications, whole blood or packed red blood cells.

The study drug is ready to use and can be administered intravenously directly or after dilution with an isotonic solution (e.g., 5% glucose or 0.9% sodium chloride). Albumin solutions should not be diluted with water for injections as this may cause haemolysis in the treated patients.

The solution should be clear or slightly opalescent. Infusion solutions that are cloudy or have sediment should not be used. This may suggest that the product is unstable or the solution is contaminated. After opening the packaging of each vial, the solution should be used immediately.

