7.2 Time of randomisation

Randomisation leads to the assignment of a participant to the albumin group or to the control group without albumin.

The randomisation day is defined as the treatment day on which the randomisation takes place. It ends when a new daily treatment sheet is created.

Randomisation must be performed within two hours of the written informed consent or confirmation of urgency of participation in the clinical trial with possible benefit to the patient by an independent consultant or other procedures established in the trial centre to include patients who are unable to provide informed consent

The randomisation is carried out by an automated internet-based service, which is provided by the Centre for Clinical Studies Jena (ZKS). The group assignment is retrieved via a validated electronic tool (PaRANDies) by the respective trial centre. The group assignment of the patient must be documented (patient record, e-CRF). Each participant will receive a randomisation number.

- Collection of data on infection, microbiology and anti-infective therapy
- Recording of clinical parameters (body temperature, respiratory haemodynamic parameters) at the time of randomisation (+/- 1 hour)
- · Recording of concomitant medication (catecholamines, inotropes, diuretics, fluid therapy including transfusion, adjunctive sepsis therapy) at the time of randomisation (+/- 1 hour)
- Collection of routine data from the laboratory (not trial-related), performed in the 24-h period before randomisation: haemoglobin, creatinine, bilirubin, C-reactive protein, procalcitonin, leucocytes, platelets, lactate, arterial blood gas analysis (PaCO2, PaO2, FiO2, SO2, pH, ScO2)
- Recording of intensive care interventions (ITN, CVC, AC, RRT, ventilation, ECMO, haemodynamic monitoring) at the time of randomisation (+/- 1 hour)
- Start capturing AEs, SAEs, sepsis-related clinical events

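### The entry criterion does not secure a start dose 6-24 h after shock onset: it has no lower bound, leaves inclusion undefined, and for very early patients conflicts with the two 2-hour limits

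*Protocol*

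**What the plan says.** Protocol 5.1.2 requires "Onset of septic shock less than 24 hours prior to study inclusion", and the same sentence gives the reason: "so that administration of the initial dose of the trial product is possible within 6-24 hours after the onset of septic shock". The synopsis in 1.1 carries the same criterion. Neither place gives a minimum time since onset, and neither ties inclusion to consent, randomisation or any other recorded event. The shock definition asks that vasopressors be needed to hold mean arterial pressure at 65 "mm Hg for at least 1 hour", so a patient can qualify early.

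Three further timing rules apply:

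- Section 6.3.1: the start dose "must be started within 6 to 24 hours after the beginning of the septic shock".
- Section 6.3.1: "A maximum of 2 hours may elapse between randomisation and the start of administration of the initial dose".
- Section 7.2: "Randomisation must be performed within two hours of the written informed consent". The same limit runs from the independent consultant's confirmation or a local equivalent.

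The visit schedule (1.6) applies the 2 h dosing limit and the 6-24 h window together.

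Two passages use a different clock. The study-population line in 1.1 counts patients "within 24 hours of septic shock diagnosis". Section 5.2.2 says that a benefit can probably be shown only "if the clinical trial is started within the first few hours of the diagnosis of septic shock".

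The hypothesis in 2.1 concerns albumin started 6-24 h after onset, and 2.2 justifies that window by a subgroup of an earlier albumin trial. On analysis, SAP 2.1 keeps every randomised patient who has any later data. Protocol 11.3.1 leaves the details of deviations to the SAP, and SAP 2.5 names only additional albumin.

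**The concern.** The criterion presents onset under 24 h as enough to make a start at 6-24 h possible. That inference fails at the early end and is not assured at the late end. A site can apply the numeric criteria correctly and still hold a patient for whom one of the timing rules must give way, and no passage says which.

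What is at stake is the link between the hypothesis and the treatment delivered. Section 2.1 separates patients treated at 6-24 h from those treated earlier, so an early starter belongs to the group that the rationale sets aside. A start dose outside the window can occur only in the albumin arm. Such patients stay in the primary analysis, and their status in the per-protocol set is not stated, so it would have to be settled later in an open-label trial.

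**Working it through.** No statistical figure in the plan is involved. The check adds up the stated limits.

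**Inputs**, in hours after onset: C = consent (or its substitute), R = randomisation, D = start of the first dose.

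- 7.2: C ≤ R ≤ C + 2
- 6.3.1: R ≤ D ≤ R + 2
- 6.3.1: 6 ≤ D ≤ 24
- 5.1.2: inclusion before 24, with no lower limit

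**Early end.** D can be at most R + 2, so D ≥ 6 needs R ≥ 6 − 2 = 4. R can be at most C + 2, so R ≥ 4 needs C ≥ 4 − 2 = 2. Example: with consent at 1 h, randomisation is due by 1 + 2 = 3 h and the dose by 3 + 2 = 5 h, which is short of 6 h. The example takes onset as the start of the vasopressor need; the protocol does not define it.

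**Late end.** D cannot precede R, so R > 24 makes compliance impossible. D ≤ 24 holds for every permitted delay only if R + 2 ≤ 24, that is R ≤ 22. In terms of consent, C + 2 + 2 ≤ 24 gives C ≤ 20. What the criterion admits depends on the meaning of inclusion:

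- If it means randomisation, R stays below 24, and the two 2 h limits by themselves would let D run to just under 26.
- If it means consent, C stays below 24, R may run to just under 26, and the 2 h limits would let D run to just under 28. Example: consent at 23 h, randomisation by 25 h, dose by 27 h. A patient consented after 22 h can be randomised after 24 h with 7.2 fully kept.

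**All limits together, by time of randomisation:**

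| R (h after onset) | Can 6.3.1 be met in full? |
|---|---|
| below 4 | No: latest permitted start is before 6 h |
| 4 to below 6 | Yes, if the dose is held until 6 h |
| 6 to 22 | Yes, for any permitted delay |
| above 22 to 24 | Yes, if the dose starts within 24 − R hours |
| above 24 | No (reachable only if inclusion precedes randomisation) |

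**Share of patients.** The documents give no distribution of onset-to-consent or onset-to-randomisation times. The registry review in 4.2 counts patients within 24 h of onset but does not say when within that period they would have been enrolled. The affected share cannot be computed.

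**The case against.** The strongest reply is that the purpose clause in 5.1.2 is itself a condition. Together with the mandatory wording of 6.3.1 and the repeats in 1.6 and 7.3, it tells a site not to include a patient at a moment when the dose cannot fall in the window. Section 5.1 asks for daily screening, and nothing obliges a site to obtain consent the moment criteria are met, so a site can time its steps to satisfy every limit. This stands in part: the rule is implicit rather than absent. It does not close the gap, because the clause gives no lower bound, no defined starting event and nothing that can be checked, while 5.2.2 favours an early start.

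The late end is weaker than a reader might infer. The 2 h figures are maxima, and a patient consented at 23 h can still be dosed by 24 h. A start at 27 h would itself breach 6.3.1. Only randomisation after 24 h rules out compliance.

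Nor must every conflict put an albumin patient outside the window. A site that delays randomisation beyond 2 h after consent breaches 7.2 before allocation, hence in both arms, and can still dose within 6-24 h.

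The consequence is also limited. The primary objective in 3.1 does not mention the start window. The timing signal quoted in 2.1 has p = 0.2. A mistimed first dose can still be followed by titrated albumin for up to 28 days in the ICU. The diagnosis wording in 1.1 is a summary line; the synopsis criterion itself counts from the start of shock.

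**Conclusion.** The inconsistency holds and should be corrected. In hours, its size is exact: the limits cannot all be met for randomisation before 4 h or consent before 2 h; a late start becomes possible for randomisation after 22 h and unavoidable after 24 h. These bounds assume only that the 2 h limits and the 6-24 h window are binding and measured on one clock from onset.

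In patients, the size is unknown. A reader might turn the bounds into a percentage of the albumin arm by assuming evenly spread consent times. The documents support no such distribution, and the result would also assume that sites ignore the window. A reader might also infer that part of the albumin arm will fall outside the hypothesis, or that power is lost. Neither is shown: mistimed doses are a risk, mistimed patients may still benefit, and the sample size calculation does not use the start time. What is shown is a protocol that can force a deviation, and a SAP that does not say how to treat it.

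**What to change.** Reconcile 5.1.2, 6.3.1, 7.2 and the synopsis. The sponsor decides which limit gives way.

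- Define inclusion as one recorded event.
- State lower and upper bounds on time from onset to randomisation that follow from the start window and delay limits the sponsor confirms. With the present limits, all rules can be met only for randomisation from 4 h after onset and early enough for a start by 24 h (by 22 h if the full 2 h is used).
- Use one clock in 1.1, 5.1.2, 5.2.2 and 6.3.1.
- Have the randomisation tool check the bounds from the onset time, which 7.1 already records.
- State in SAP 2.2 or 2.5 whether a start dose outside the confirmed window is a major deviation for the per-protocol set.

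The cost is wording in a few sections, one range check in the web randomisation and one SAP rule. Some patients found very early would be randomised later, and some found at the end of the window would not be randomised.

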5.1.3 Exclusion criteria

Patients who meet any of the following exclusion criteria cannot be included in the trial:

- Moribund conditions with life expectancy less than 28 days due to secondary diseases or advanced malignant disease and palliative situations with life expectancy less than 6 months
- "End of life" decisions made before obtaining informed consent: "Do Not Resuscitate (DNR)" and "Withhold/Withdraw Life-Sustaining measures"
- Previous participation in the study
- Participation in another interventional clinical trial within the past 3 months

ARISS EudraCT-Nr.: 2018-001874-89 ZKSJ0112_ARISS

- Shock states that can be explained by other reasons, e.g. cardiogenic, anaphylactic, and neurogenic shock
- History of hypersensitivity to albumin or any other component of the trial product, e.g., sodium caprylate, sodium N-acetyltryptophanate
- Disease in which the use of albumin may be deleterious, e.g., decompensated heart failure or traumatic brain injury
- Disease situations in which albumin administration may be advantageous, e.g., hepatorenal syndrome, nephrosis, burns, and intestinal malabsorption syndrome
- Lactation

